A. Study Type and Design: This is a crossover study with both PwMS and age and sex-matched neurotypical controls. 30 PwMS and 20 neurotypical controls be randomized into two groups and will participate in two split-belt treadmill training sessions while outfitted with cortical fNIRS and TENS devices on their bilateral tibialis anterior and rectus femoris. The first group will complete split-belt treadmill training with TENS OFF during the first visit and TENS ON during the second visit. The second group will complete split-belt treadmill training with TENS ON during the first visit and TENS OFF during the second visit to control for a learning effect. In between visits there will be a 4-week washout period. Participants will receive TENS only during the 10-minute split-belt adaptation period of the paradigm. During all other periods the TENS will be OFF.

B. Sample size, statistical methods, and power calculation

1. Total number of subjects who will be approached (including screen fails, controls and subject withdrawals) to reach enrollment numbers for the lifetime of the study for this investigator's site: 60
2. Total number of subjects to be enrolled at this site: 50

INSTITUTIONAL REVIEW BOARD NON-EXEMPT PROTOCOL TEMPLATE

3. Brief Description/justification for the proposed sample size in *lay terms*: From our preliminary data we computed a large effect size of 1.01 for change in brain activity in the SMA from baseline walking to split-belt treadmill training. According to our power analysis, to maintain an alpha of 0.05 and a power of 0.8, at least 10 participants per group are needed to detect significant changes in brain activity.
4. Simple randomization will occur (TENS first or TENS second) for both groups (PwMS and neurotypical controls).
5. No masking will occur in this study.

C. Subject Criteria (See Vulnerable Populations appendix 1, if applicable): PwMS and neurotypical controls from ages 18-86. All races and genders are included.

1. Inclusion criteria:

- A diagnosis of relapsing remitting multiple sclerosis OR a neurotypical adult (ages 18-86)
- Not experiencing an active relapse
- Able to stand and walk without an assistive device
- Able to walk for three tenths of a mile without stopping to rest
- MS participants must have a neurologist confirmed diagnosis of relapsing-remitting MS.
- MS participants must be independently ambulatory in the community, expanded disability status scale (EDSS) score < 5 (clinical measure of MS severity).

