- 3 Trained graduate students and the principal investigator will determine whether the subject is able to give consent. People with cognitive impairments and minors will be excluded from this study due failing to meet the inclusion/exclusion criteria.

D. Specific procedures and techniques used throughout the study

1. Laboratory tests
 - **Gait Adaptation.** This will be assessed using inertial sensors and 3-D motion capture. Both use noninvasive markers that are placed on the lower limbs of the participants. Our outcome measures assessing gait adaptation will be step length asymmetry (SLA). Step length is quantified by the anterior-posterior distance between heel markers at leading limb heel strike. Step length asymmetry will be calculated by subtracting the step length of the less affected limb from the step length of the more affected limb for each consecutive step and normalized to participant stride lengths and will be assessed continuously throughout each gait trial. We will use step length asymmetry to identify 1) the adaptation rate during the split-belt adaptation period to assess speed of adaptation between conditions and groups, and 2) adaptation savings, or the difference in adaptation rate between visit 2 and visit 1, to quantify adaptation retention between conditions and groups.

INSTITUTIONAL REVIEW BOARD NON-EXEMPT PROTOCOL TEMPLATE

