- **Cortical Activation via fNIRS.** All fNIRS data will be acquired using a mobile NIRS Sport2 device (NIRx Medical Technologies, nirx.net), which will be secured to participants' backs using backpack-like straps and buckles. This head probe was designed to measure regions of interest (ROI) that were established a priori. The Juelich atlas within the fNIRS Optodes Location Decider (fOLD) toolbox in MATLAB was used to design our optode montage which identifies channel locations above superficial components of the frontal, motor, and sensory regions. Our fNIRS head probe will include 16 sources and 15 detectors which will create 48 channels over the designated ROIs (Figure 1). Additionally, eight short-separator detectors will be used to measure scalp perfusion. All fNIRS data will be acquired and streamed to a laptop using Aurora software v.2021.9 (NIRx Medical Technologies, nirx.net/aurora). Raw fNIRS data will be processed using a commercial software tool, Satori v.1.8 by Brain Innovation (NIRx Medical Technologies, nirx.net/satori) to perform pre-processing steps, such as motion artifact removal, physiological noise detection, and channel selection and removal. Following, the raw light intensity data will be converted to optical density values and then converted to oxygenated hemoglobin (HbO), deoxygenated hemoglobin and total hemoglobin values using the Modified Beer-Lambert Law automatically through Satori software. The HbO beta values calculated from general linear models will be used as a proxy for cortical activity, and we will measure changes in HbO beta between each protocol period described in Figure 2B.

[figure not shown]

Figure 1. Optode montage (16x15) created using Brodmann atlas within fOLD to allow measurement of cortical hemodynamics for premotor, sensorimotor, and posterior parietal regions. Each red circle indicates a source optode, each blue circle represents a detector optode, and each purple connecting line represents a unique channel.

2. Study Procedures:

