3. All consent information will be stored electronically on a secure server through Colorado State University accessed only by our designated research team. Information collected electronically will be stored on a secure Colorado State University network server to prevent any breaches in confidentiality. Additionally, all questionnaires, demographics, and screening information will be stored in a REDCap database controlled by CCTSI and only approved study personnel will have access this database. Data we stored on the R:/Drive which is a secure server or on REDCap. Data will be kept for a minimum of 3 years after the completion of the study by [name].
4. People will be deidentified and all information will be used with a subject code (e.g., SBNT_000, with the key to this code available only as a physical copy stored in of locked lab.
5. [name] and [name] will have access to and maintain the key to the code.
6. Data will only be linked to a participant via a participant code.
7. All data collected, including identifiable information or personal health information will be stored either electronically on secured Colorado State University server or through a REDCap database with access restricted to study personnel. Any data not in electronic form will be stored in a locked file cabinet with access limited to study personnel. The Sensorimotor Neuroimaging Laboratory is located in Moby room 154 within the Department of Health and Exercise Science. All hard copy data will be stored in the Sensorimotor Neuroimaging Laboratory, with access being restricted to authorized key holders and key study personnel.
8. No mobile devices will be used for collection or storage of data.
9. N/A. No identifiable data will be sent outside of CSU.

B. Sample / Specimen Collection: N/A

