- C. Statistical Analysis Plan:** In this crossover design, PwMS and healthy control participants will be pseudo-randomized to begin in either the TENS First or TENS Second condition. Randomization will be performed using a random number generator and will be counterbalanced across age, sex, and fast limb to ensure group balance. A predefined list of participant numbers with corresponding randomized assignments will be generated prior to enrollment. Linear mixed-effects models will be used to identify differences in adaptation and fNIRS outcomes, with group (PwMS vs. healthy controls), visit (Visit 1 vs. Visit 2), and TENS condition (TENS ON vs. TENS OFF), along with their interactions, as fixed effects, and participant number as a random effect. Assumptions of linearity, normality of residuals, and homoscedasticity will be tested for each model. Following model creation, a repeated measures ANOVA will be performed for each adaptation outcome (adaptation rate and adaptation savings) and for cortical activation (HbO beta). Type III ANOVAs with Satterthwaite's method for degrees of freedom estimation will be used for all analyses. Post-hoc comparisons will be conducted using estimated marginal means (EMM) to further investigate significant main effects and interactions. P-values will be corrected using the Benjamini–Hochberg false discovery rate within each outcome and group when applicable. Cohen's d will be calculated to quantify effect sizes. Separate regression models will be conducted to assess the influence of demographic covariates on primary outcome models. All statistical analyses will be conducted using the lme4 and emmeans packages within R and were two-tailed with an alpha threshold set at 0.05.

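### The no-masking rule makes no exception for outcome processing, and no processing rules are given, so TENS ON and OFF sessions could be processed differently

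*Combined protocol and SAP*

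**What the plan says.** Section II.B.5 is a single sentence: "No masking will occur in this study". It separates no roles and gives no reason.

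The randomised contrast is TENS ON against TENS OFF in a two-visit crossover. Section II.A describes one sequence as follows: "The first group will complete split-belt treadmill training with TENS OFF during the first visit and TENS ON during the second visit". The other sequence reverses the order. The Statistical Analysis Plan (V.C) tests that contrast on both the adaptation and the fNIRS outcomes, with "TENS condition (TENS ON vs. TENS OFF), along with their interactions, as fixed effects, and participant number as a random effect".

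Both kinds of outcome are derived after the session:

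- **fNIRS (III.D.1, Cortical Activation).** Commercial software is used "to perform pre-processing steps, such as motion artifact removal, physiological noise detection, and channel selection and removal". No thresholds or rejection rules are given. The one step described as automatic is the later conversion to haemoglobin values, done "using the Modified Beer-Lambert Law automatically through Satori software".
- **Gait (III.D.1, Gait Adaptation).** Step length asymmetry is used to identify "the adaptation rate during the split-belt adaptation period to assess speed of adaptation between conditions and groups", and also savings, the visit 2 rate minus the visit 1 rate. No model, time window or estimation rule is given for the rate.

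The coding that exists protects identity. IV.A.6 says "Data will only be linked to a participant via a participant code". V.C says "A predefined list of participant numbers with corresponding randomized assignments will be generated prior to enrollment". A participant number therefore points to a sequence, and nothing says that the list is kept from those who process data.

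**The concern.** Participants and treadmill staff are hard to mask here: stimulation is set just below motor threshold, and the risk section (III.H) says that it may be felt. The person who later cleans a recording or computes a rate is different, because that work can be done without knowing the condition.

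Three features of the plan make this worth attention. The processing rules are not written down. Nothing hides the condition from the processor. The study objectives (I.A.2) predict that TENS will increase symmetry gains and retention. In that setting, small choices that differ between ON and OFF sessions would pass straight into the randomised contrast. Randomisation and the crossover do not protect against this, because a processing shift tied to the condition follows the condition through both sequences.

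**Working it through.** **Step 1. The plan's own figure.** Masking changes no sample size, but the plan's one power statement (II.B.3) is a useful check on the method. Inputs: effect size 1.01, alpha 0.05, power 0.8, at least 10 per group. For a two-sided paired t-test, power = P(|T| > t(0.975, n−1)), where T is noncentral t with n−1 degrees of freedom and noncentrality d√n.

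- n = 10: noncentrality 1.01 × √10 = 3.194, critical value 2.262, power 0.811.
- n = 9: noncentrality 1.01 × √9 = 3.03, critical value 2.306, power 0.756.

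The stated 10 reproduces. That effect is the SMA change from baseline walking to split-belt walking. It is not a TENS effect, so it says nothing about the size of the ON-OFF contrast.

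**Step 2. What a processing shift would do.** Suppose that TENS has no true effect and that processing moves the mean ON-OFF difference by b, in SDs of the within-person difference. The same formula applies with noncentrality b√n. The values of b are assumptions; the documents supply none. The sample sizes are from II.A: 30 people with MS, 20 controls, 50 pooled. (The TENS Protocol section says 30 controls; this does not affect the point.)

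Worked case, n = 30, critical value 2.045:

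- b = 0.1: noncentrality 0.1 × √30 = 0.548. Upper tail 0.0763 plus lower tail 0.0064 gives 0.083.
- b = 0.2: noncentrality 0.2 × √30 = 1.095. Upper tail 0.1839 plus lower tail 0.0013 gives 0.185.

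| Assumed b | n = 20 | n = 30 | n = 50 |
|---|---|---|---|
| 0 | 0.050 | 0.050 | 0.050 |
| 0.1 | 0.071 | 0.083 | 0.107 |
| 0.2 | 0.136 | 0.185 | 0.284 |
| 0.3 | 0.247 | 0.355 | 0.548 |

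**Step 3. Does the paired test mislead by ignoring visit?** V.C includes visit in the model. Savings is visit 2 minus visit 1, so a shift of b in ON sessions moves savings by +b in the OFF-then-ON sequence and by −b in the other, a gap of 2b. With 15 per sequence (assumed, equal split of 30), a two-sample comparison has noncentrality 2b ÷ √(2/15) = b√30, as in Step 2. With 28 degrees of freedom the results are 0.083 and 0.185 again. Adjusting for visit neither removes nor enlarges the effect of the shift.

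**Step 4. Which comparisons are exposed.**

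| Comparison | Randomised? | Direction predicted for TENS? |
|---|---|---|
| Adaptation rate and savings, ON vs OFF | Yes | Yes (I.A.2) |
| HbO beta, ON vs OFF | Yes | No |
| HbO beta, split-belt vs tied-belt | No, periods within a session | Not a TENS comparison |

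The first row is the most exposed. In the second, processing could still differ by condition, but no stated expectation gives it a direction. The third is outside the point.

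**The case against.** The strongest reply is that the plan shows unspecified rules, not demonstrated judgement. It does not say whether channels are rejected by hand or by fixed software settings, it names an adaptation rate without describing a curve fit, and it does not mention excluding strides. If fixed rules are applied identically to every session, little room for bias remains. This stands: a reader might infer that processing is known to be subjective, and the documents do not support that. They also do not say that the rules are fixed.

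A reader might also infer that such a bias could never be found or corrected. That is not supported. Processing is applied to recorded raw signals, and IV.A.3 keeps data for at least 3 years after completion. Exclusions could be compared by condition and files reprocessed, although this costs more, and persuades less, once results are known.

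The shift is assumed, and a simple paired test stands in for the mixed model of V.C. This is also correct; the figures show sensitivity and do not estimate a bias.

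Finally, masked processing is not costless. III.N.1 describes monthly rolling review to support preliminary results and grant preparation, which one lock at the end of the study would obstruct. Staff who ran a session may remember its condition, and visible stimulation artifact could reveal it. These points shape the remedy and do not remove the reason for it.

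**Conclusion.** The point holds as an inexpensive improvement to the design, not as a demonstrated flaw. A blanket rule of no masking, together with absent rules for artifact removal, channel rejection and rate derivation, leaves the randomised ON-OFF comparison open to processing that differs by condition. The case is strongest for adaptation rate and savings and weaker for HbO beta under ON versus OFF. It does not extend to split-belt versus tied-belt activation, the effect on which the study is powered.

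The size of any bias is unknown. On the assumption of a 0.1 or 0.2 SD shift, a true null and a paired test at two-sided 0.05, type I error at n = 30 is about 0.08 or 0.19. Nothing in the documents shows that a shift of this size, or any shift, will occur.

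**What to change.** Keep the open-label conduct of sessions and change the processing:

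1. Write the artifact, channel-rejection and adaptation-rate rules into III.D.1 and V.C before processing starts, and apply them identically to all sessions.
2. Process files under neutral codes that hide TENS condition and sequence. The existing participant number will not serve, because the allocation list links it to an assignment.
3. Log every exclusion, so that counts can be compared by condition later.
4. Release the condition key only after each batch is locked. Both visits of a participant should be in the same batch, since revealing one visit reveals the other.
5. Amend II.B.5 to say that outcome processing is masked to TENS condition, and mirror this in III.D.1 and V.C.
6. Run the monthly review in III.N.1 on locked batches or on data pooled across condition. Adverse event review is unaffected.

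The cost is protocol wording, a small file-coding task and some delay before results can be viewed by condition. Someone who does not process the data should hold the key; the documents do not show whether the present team includes such a person. Masking may be only partial if session staff also process data or if stimulation artifact is visible, so the fixed rules in item 1 matter as much as the coding.

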2. Multiple sclerosis affects all races, all genders, and all ages, but is most prevalent in women of Northern European descent. This study will recruit individuals with multiple sclerosis, with no restrictions for race or gender. We therefore expect the study population to reflect the general demographics of multiple sclerosis. Our lab group is well versed in the nuances of minority population enrollment to facilitate equity recruitment and in clinical trial participation. Our inclusion criteria of 18-86 years were chosen for comparison of clinical and biological differences between individuals with multiple sclerosis and neurotypical controls across a variety of age groups. These age groups will allow us to detect meaningful differences between individuals with multiple sclerosis and neurotypical controls across the lifespan. Additionally, we will be poised to identify changes in function as a result of multiple sclerosis and will be able to avoid age as a confounding factor due to age and sex matching. Our lab group has previously studied multiple sclerosis among this age range for 10+ years and have the necessary accommodations (e.g., bodyweight harness, handrails, wheelchairs) for all levels of disability status.
3. Over 100,000 people within the Colorado-Wyoming region are afflicted with MS and participant recruitment will be determined in consultation with [name] from the Department of Neurology / Rocky Mountain MS Center at the University of Colorado where over 8,000 patient visits are conducted annually. Participants will be recruited from the UC Health Regional Neuroscience Center at Poudre Valley Hospital and the Multiple Sclerosis Center of the Rockies in Fort Collins as well as the Local National MS Society and other local MS and general Neurology clinics. Potential participants will be identified through word of mouth, clinician support, or flyers. Interested participants will be contacted via email or telephone where they will be informed in greater detail what the study involves. Following an explanation of the study potential participants will be asked if this particular study is of interest to them and if so a screening for eligibility will be scheduled.
4. In Kuali, we have attached a copy of a flyer that will be distributed via email to people at the Brain Health Center of the Rockies, the Center for Healthy Aging, and the Colorado-Wyoming chapter of the National Multiple Sclerosis Society.

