- **TENS Protocol.** 30 PwMS and 30 age- and sex- matched controls will be randomized into two groups and complete two split-belt treadmill training sessions identical to Aim 1, while outfitted with cortical fNIRS and TENS devices on their bilateral tibialis anterior and rectus femoris. The first group will complete split-belt treadmill training with TENS OFF during the first visit (these are the participants in Aim 1) and TENS ON during the second visit. The second group will complete split-belt treadmill training with TENS ON during the first visit and TENS OFF during the second visit to control for a learning effect. In between visits there will be a 4-week washout period (Figure 3). Participants will receive TENS only during the 10-minute split-belt adaptation period of the paradigm. During all other periods the TENS will be OFF. We will use an FDA-approved clinical TENS device, the LG-TECELITE Therapy System (LGMedSupply, Cherry Hill, NJ). Stimulation will consist of bursting biphasic pulses delivered with electrode pairs (2 in. \times 4 in. pads) placed on the skin over the

INSTITUTIONAL REVIEW BOARD NON-EXEMPT PROTOCOL TEMPLATE

stimulated muscles. The stimulus frequency will be set at 5 Hz with a seven pulses of 0.15 ms based on recent evidence suggesting that bursting TENS is most effective for improving walking performance and limits nerve accommodation to the stimulation. The amplitude of the TENS stimulation will be individualized for each participant in accordance with their specific motor threshold. The TENS amplitude will be slowly increased at 1 mA increments on each individual muscle until non-voluntary muscle contractions can be seen or felt by the investigator, then the amplitude will be set to 2 mA below the motor threshold for each muscle and limb during the split-belt adaptation period. Additionally, we are choosing to outfit TENS on the tibialis anterior and rectus femoris due to previous studies successfully improving gait performance in PwMS using these stimulation locations (Figure 3).

[figure not shown]

Figure 3. (Left) Study design schematic including randomization and TENS condition at each visit. (Right) Example of TENS electrode placement on the bilateral tibialis anterior and rectus femoris.

- **Clinical Assessments**

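### The group comparison relies on age and sex matching that is not defined, and the primary models contain neither age nor sex

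*Combined protocol and SAP*

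**What the plan says.** Section II.A describes the design: "This is a crossover study with both PwMS and age and sex-matched neurotypical controls". It then gives the numbers: "30 PwMS and 20 neurotypical controls be randomized into two groups". Section II.B.2 agrees with a total of 50: "Total number of subjects to be enrolled at this site: 50". The TENS Protocol in III.D.2 gives a different control number: "30 PwMS and 30 age- and sex- matched controls will be randomized into two groups".

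Section III.A.2 (Recruitment) states the benefit expected from matching, namely that the study "will be able to avoid age as a confounding factor due to age and sex matching". The same paragraph says of the ages enrolled: "These age groups will allow us to detect meaningful differences between individuals with multiple sclerosis and neurotypical controls across the lifespan".

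Section V.C (Statistical Analysis Plan) lists the fixed part of the mixed models: "with group (PwMS vs. healthy controls), visit (Visit 1 vs. Visit 2), and TENS condition (TENS ON vs. TENS OFF), along with their interactions". The only random effect is participant. On demographics it says: "Separate regression models will be conducted to assess the influence of demographic covariates on primary outcome models". The covariates are not named. Counterbalancing on age and sex in V.C applies to the order of the TENS conditions, not to PwMS versus controls.

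**The concern.** Section I.A.2 wants group differences that can be put down to MS. Randomisation protects the TENS order, but it does nothing for the PwMS-versus-control contrast. That contrast depends on matching, on adjustment, or on both.

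The matching is not pinned down. The control number is 20 or 30 depending on the section, and nothing says whether matching is individual or by frequency, at what ratio, within what age tolerance, or what happens when no match is found. The eligible ages run from 18 to 85 or 86, and III.A.2 itself notes that MS is most common in women, so controls recruited without a working rule could differ in age or sex.

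The primary models then make no use of the matching variables. Either an imbalance that remains passes into the group estimate, or matching succeeds and the analysis ignores the precision that it bought.

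**Working it through.** **The plan's own figure.** II.B.3 gives 10 per group for an effect size of 1.01, alpha 0.05 and power 0.8. A two-sided paired t-test gives n = 9.79, rounded up to 10, with power 0.811 at n = 10. The figure reproduces, but it concerns a within-person change in cortical activity. It says nothing about the PwMS-control contrast.

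**Matching arithmetic.**
- 30 and 20 (II.A): at most min(30, 20) = 20 one-to-one pairs, leaving 30 − 20 = 10 PwMS (33%) without a partner. Frequency matching at 3:2 is feasible but not stated.
- 30 and 30 (III.D.2): 30 pairs are possible.

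**Terms in the models.** Group, visit, TENS condition and their interactions are fixed, and participant is random. Age, sex and matched set do not appear.

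**Case A: matching works.** Assumptions, since the documents give no figures: one outcome value per person with SD 1; age-outcome correlation r = 0.3 to 0.5; controls exactly age-matched to PwMS; any unpartnered PwMS are ordinary draws from the same MS population. With m controls:
- SE used by the unadjusted test = √(1/30 + 1/m)
- True SE = √[ r²(1/m − 1/30) + (1 − r²)(1/30 + 1/m) ]
- Actual error rate ≈ 2 × P(Z > 1.96 × SE used / true SE)

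| Controls | r | SE used | True SE | Actual error rate, formula | Simulation |
|---|---|---|---|---|---|
| 20 | 0.3 | 0.289 | 0.278 | 4.2% | 4.2% |
| 20 | 0.5 | 0.289 | 0.258 | 2.8% | 3.0% |
| 30 | 0.3 | 0.258 | 0.246 | 4.0% | 3.7% |
| 30 | 0.5 | 0.258 | 0.224 | 2.4% | 2.5% |

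Formula and simulation agree within 0.3 percentage points. The standard error is too large because the test ignores the shared ages. With age in the model, the simulated error rate returns to about 5%.

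Power was simulated at the difference that an unadjusted two-sample t-test detects with 80% power (d = 0.83 for 30 and 20; d = 0.74 for 30 and 30). It is about 81-83% without age and about 83-90% with age. Age accounts for r² = 9% to 25% of between-person variance under these assumptions.

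**Case B: matching is incomplete in one direction.** Assume age SD 15 years, r = 0.3 to 0.5, 20 exact pairs, and 10 unpartnered PwMS who are on average 6 to 18 years older (or younger).
- Group mean age gap = 6 × 10/30 to 18 × 10/30 = 2 to 6 years
- Bias = (2/15) × 0.3 to (6/15) × 0.5 = 0.04 to 0.20 SD, against SE 0.289
- Error rate from a normal shift of bias/SE: 5.2% to 10.7%

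This range depends entirely on the assumed one-directional gap. If the 10 are ordinary draws, the standard error of their mean age difference from the other 20 is 15 × √(1/10 + 1/20) = 5.8 years. A gap of 18 years would then be 18/5.8 = 3.1 standard errors.

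**The case against.** The strongest reply has five parts.

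1. *The plan says matched, not matched one to one.* This stands. A reader might infer that 30 PwMS cannot be matched to 20 controls at all. Only one-to-one matching is impossible, and with the 30 controls in III.D.2 even that difficulty disappears. What remains is that the number is unreconciled and the rule is missing.

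2. *With successful matching, the unadjusted contrast is not confounded by age.* This stands as well. Ignoring the match then costs precision, not validity, as Case A shows. A reader might infer from Case B that false positives are inflated. The documents contain nothing to show that unpartnered PwMS would differ systematically in age.

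3. *The separate regressions are a provision for demographics.* In part. The sentence could mean refitting the primary models with covariates. But it names no covariates and does not say how the group estimate would be revised, so it does not secure the assurance in III.A.2. Nor does the text show that those regressions would leave the estimate untouched.

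4. *The explicit hypotheses are within-person.* This stands and limits the point. Age and sex are fixed for a person, so they do not confound split versus tied belts or TENS ON versus OFF. I.A.2 also compares the TENS effect between groups. That is a group-by-TENS interaction, which age and sex main effects leave essentially unchanged.

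5. *The lifespan sentence explains the eligible age range and does not promise a group-by-age test.* This is a fair reading. It calls for a label, not a power calculation.

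**Conclusion.** The point holds for the PwMS-versus-control contrast. The assurance about age rests on a matching scheme that is undefined and has two control numbers, and the primary models do not adjust for the matching variables.

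The size is modest. If matching works, the nominal 5% group test runs at roughly 4% (r = 0.3) down to 2.5-3% (r = 0.5), and about 2 to 7 percentage points of power are given up near the detectable limit. If matching is incomplete in one direction, the bias depends on a gap that the documents do not give. Cases A and B both rest on the assumed correlation, and Case B also on an assumed age SD and age gap. They illustrate age only; sex was not modelled.

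The documents do not support the stronger conclusion that the group comparison is confounded, or that its error rate is known to exceed 5%. Age adjustment is worthwhile under either control number.

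**What to change.** 1. In V.C, include age (continuous) and sex as fixed effects in every primary mixed model that yields a PwMS-versus-control contrast. Keep any further demographic regressions as sensitivity analyses, with the covariates named.
2. Reconcile the control number in II.A and II.B.2 with that in III.D.2, and state the matching ratio that follows from it.
3. In III.A.2, replace the sentence on age confounding by a statement that the groups are matched on, and adjusted for, age and sex. Label age-specific group differences as exploratory.

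The cost is two between-person degrees of freedom (with 30 and 20, from 50 − 2 = 48 to 46) and a softer claim. Demographic information is already collected at screening (III.B), and the adjustment itself needs no extra participants. The change does not alter the within-person contrasts or, in any material way, the group-by-TENS interaction.
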